8.3 ADVERSE EVENTS AND SERIOUS ADVERSE EVENTS

The definitions of an AE or SAE can be found in [Appendix 5](#).

Investigators will seek information on AEs at each participant contact until at least 100 days after the last dose of study intervention. AEs reported by the participant (or, when appropriate, by a caregiver, surrogate, or the participant’s legally authorized representative) or noted by study personnel, will be recorded in the participant’s medical record and on the Adverse Event eCRF page. If the AE is determined to meet seriousness criteria, the event will be reported as an SAE on the study-specific SAE Report Form (SAERF) within 24 hours of awareness. Seriousness criteria is defined in [Appendix 5](#).

The Investigator and any qualified designees are responsible for detecting, documenting, and recording events that meet the definition of an AE, AESI (as applicable), or SAE and remain responsible for following up AEs that are serious, considered related to the study intervention or study procedures, or that caused the participant to discontinue the study intervention (see [Appendix 5](#)).

8.3.1 Time Period and Frequency for Collecting AE, SAE, and Other Reportable Safety Event Information

All SAEs will be collected from the time the participant signs informed consent until at least 100 days after the last dose of study intervention. Prior to initiation of study intervention, only SAEs that are-related to a protocol-mandated intervention, including those that occur prior to the assignment of study procedures (eg, screening invasive procedures, such as biopsies) should be reported. After obtaining informed consent, but prior to initiation of study intervention, other medical occurrences will be recorded as medical history.

All AEs, including AESIs (as applicable), will be collected from the start of study intervention until at least 100 days after the last dose of study intervention.

If the Investigator learns of any SAE, including a death, at any time after the end of the AE reporting period, and he/she considers the event to be reasonably related to the study intervention or study participation, the Investigator must promptly notify the Sponsor or its designee. The Investigator should report these events directly to the Sponsor or its designee, either by faxing or emailing the SAERF.

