3 STUDY DESIGN

[figure not shown]
PICI0033 is an open-label, non-randomized, exploratory platform protocol designed to assess the safety and antitumor activity of multiple immunotherapy combinations in participants with metastatic castration-resistant prostate cancer (mCRPC) who have received prior therapy. Each cohort of the platform study will consist of up to 2 stages: Stage 1, an initial stage to evaluate safety, biomarkers, and clinical activity of a combination and Stage 2, an expanded cohort, when warranted, based on the safety, clinical activity, and/or biomarker results from Stage 1. The Sponsor intends to modify and/or add new combinations to the protocol as data emerge from this and other trials.

This is not a randomized study. Assignment to one of the immunotherapy combinations will be made by the Investigator using his/her best clinical discretion based on the participant's medical history and disease status and knowledge of the available immunotherapy combination cohorts open for enrollment. The dose and schedule selected will be described in the protocol cohort appendix for each respective combination (eg, Appendix Cohort A, Appendix Cohort B, etc.). The duration of immunotherapy combination study intervention will be dependent on the combination administered. Participants will be followed for up to 2.5 years from the time of the initiation of study intervention.

The study is not intended or powered for hypothesis testing or comparison between cohorts. The study is intended to provide preliminary estimates of adverse event (AE) rates, response rates, effect sizes, and confidence intervals (CIs) to aid the design of later studies. Approximately 15 participants, including a minimum of 7 with a non-bone metastatic lesion that can be biopsied, will be enrolled in each immunotherapy combination cohort in Stage 1. An additional approximately 15 participants, including a minimum of 7 with a non-bone metastatic lesion, will be enrolled in Stage 2 if the cohort is expanded.

The general study schema is depicted in Figure 1.

Figure 1: Study Schema

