3.2 Study Objectives and Endpoints

The study objectives and endpoints for the Core Protocol are listed in Table 1. Any cohort-specific endpoints will be captured in an appendix to this SAP.

Table 1: Objectives and Corresponding Endpoints

Objectives	Endpoints
Primary	

 To determine the safety of each immunotherapy combination in participants with mCRPC. 	
 Incidence and severity of AEs.
Secondary	

 To determine the CRR of each immunotherapy combination in participants with measurable mCRPC. 	
 Composite Response Rate (CRR): A composite endpoint where response is defined as a participant meeting at least one of the following:

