3.4 Analysis Timing

The primary analyses described in the main body of this document will be performed for each immunotherapy combination cohort separately after all participants for a specific cohort have at least 6 months of follow-up from the date of first dose or have discontinued the study. Each cohort will be assessed independently of the other cohorts, and the data from each cohort will be analyzed separately. Study conduct of one or more cohorts may be ongoing at the time of final analysis for a given cohort.

Any cohort-specific modifications to the statistical methods, including any additional cohort-specific endpoints, will be captured as an appendix in this SAP.

Analysis of safety and efficacy endpoints will be performed prior to the time of primary analysis. These analyses will help inform adaptations of the trial, such as expanding, modifying, or terminating a cohort. More information about these interim analyses is presented in Section 5.7. These results may be presented and/or published prior to the primary analysis.

A cohort will formally end once all participants have been followed for survival status for a maximum of 2.5 years or until death, withdrawal of consent, or loss to follow-up. The Sponsor may choose to discontinue survival follow-up of a cohort at any time. A survival analysis of long-term follow-up may be performed after the primary analysis has been completed.

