5.5.2 Adverse Events

All reported AEs will be coded using the latest version of the Medical Dictionary for Regulatory Activities (MedDRA) and graded using the NCI Common Terminology Criteria for Adverse Events (CTCAE) version 5.0.

A treatment-emergent adverse event (TEAE) is defined as any event that either occurs after the initiation of study intervention, having been absent at baseline, or, if present at baseline, appears to have worsened in severity or frequency, whether or not the event is considered related to study intervention. AEs assessed by the Investigator to be “Possibly”, “Probably”, or “Definitely” related to any study intervention, as well as AEs with missing relationship, will be considered treatment related.

Handling of missing and partial missing AE dates is described in Section 5.6.1.

The incidence of TEAEs will be summarized (overall, by system organ class and preferred term and by severity) by cohort. In addition, separate summaries will be generated for SAEs, deaths, treatment-related AEs, AEs leading to treatment discontinuation, and AEs leading to temporary interruption and/or dose reduction. Participant deaths and the primary cause of death will be listed.

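### SAP 3.4 allows the primary AE analysis to run while some 100-day AE windows are still open, and specifies no later AE analysis

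*SAP*

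**What the plan says.** The only primary endpoint is "Incidence and severity of AEs" (SAP 3.2, Table 1); SAP 5.4.1 confirms that no efficacy endpoint is primary.

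SAP 3.4 times the primary analyses cohort by cohort, when all participants "have at least 6 months of follow-up from the date of first dose" or have left the study. The clock starts at first dose.

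Protocol 8.3.1 ties AE collection to last dose: AEs "will be collected from the start of study intervention until at least 100 days after the last dose of study intervention". SAP 5.5.2 sets no upper time limit on a treatment-emergent AE, which is "any event that either occurs after the initiation of study intervention, having been absent at baseline" or which worsened from baseline.

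On what follows the primary analysis, SAP 3.4 offers one sentence: "A survival analysis of long-term follow-up may be performed after the primary analysis has been completed". The same section also says "Study conduct of one or more cohorts may be ongoing at the time of final analysis for a given cohort", but defines no final analysis separate from the primary one. SAP 5.5 (safety) and 5.7 (interim analyses) add no later safety run.

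Treatment length is not fixed in either document: "The duration of immunotherapy combination study intervention will be dependent on the combination administered" (SAP 3). The cohort appendices that set it are not part of the material reviewed.

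**The concern.** The analysis trigger counts from first dose and the endpoint's observation window counts from last dose, and nothing in the SAP links the two. A participant who was enrolled late, or who stays on treatment, can be tabulated before his AE window has closed. The events that follow are still collected and still meet the SAP's definition of treatment-emergent, yet no planned table receives them.

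At stake is the main quantity the study exists to estimate. SAP 3.3 says the purpose is to give preliminary AE rates and confidence intervals for designing later studies. The proportion of treated participants with a given AE can only stay the same or rise as windows close, so any error is in one direction.

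**Working it through.** **Inputs from the documents:** trigger of at least 6 months from first dose (SAP 3.4); AE window to 100 days after last dose (Protocol 8.3.1); 15 participants in Stage 1 (SAP 3.3); survival follow-up of up to 2.5 years, or 30 months (SAP 3.4). **Assumed, because the documents do not give them:** treatment duration T, accrual period A (uniform), and AE onset at a constant hazard. One month is 30.44 days, so 6 months = 182.6 days and 100 days = 3.29 months.

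**1. The plan's own figures.** The SAP gives no figure for completeness of AE follow-up. Its precision figures for the endpoint, the exact 95% intervals in SAP Table 2, reproduce. For 6/15 the Clopper-Pearson limits are the 0.025 quantile of Beta(6, 10) and the 0.975 quantile of Beta(7, 9), which give 16.3% and 67.7% as printed. All 12 intervals agree to 0.1 point.

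**2. When a window is closed.** At exactly 6 months of follow-up the window is complete only if last dose + 100 ≤ 182.6, so the last dose must fall by about day 82.

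**3. Share of a cohort with an open window, exponential treatment duration.** Follow-up at the trigger is uniform from 6 to 6 + A months. With λ = ln 2 / median and a = 6 − 3.29 = 2.71:

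share open = [exp(−λa) − exp(−λ(a + A))] / (λA)

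For a median of 6 months and A = 6, λ = 0.1155, and (0.731 − 0.365) / 0.693 ≈ 0.53.

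| Median treatment (months) | A = 6 months | A = 12 months |
|---|---|---|
| 2 | 16% | 9% |
| 3 | 29% | 18% |
| 4 | 39% | 26% |
| 6 | 53% | 40% |

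The range is 9–53%, or about 1 to 8 of 15. For the last-enrolled participant the share is exp(−λa), from 39% (median 2) to 73% (median 6). The calculation already gives earlier enrollees their longer follow-up. It ignores death and withdrawal, which end collection and would lower these shares.

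**4. The same share with fixed treatment duration.** Share open = (T + 3.29 − 6) / A, limited to 0–1. With A = 12:

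- T = 2.5: 0 of 15
- T = 6: 3.29 / 12 = 27.4%, or 4.1 of 15
- T = 12: 9.29 / 12 = 77.4%, or 11.6 of 15

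For T = 6 the count is 8.2 of 15 if A = 6 and 2.7 of 15 if A = 18.

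**5. Effect on AE incidence.** An open window is not a missed event. Let R be the true risk over the full window W = T + 3.29. A participant followed for f months shows 1 − (1 − R)^(min(f, W)/W). The table averages this over f uniform from 6 to 18 (A = 12); the last column shows what a hard 6-month cap on everyone would give.

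| T (months) | True 20% shows as | True 40% shows as | True 40% under a hard 6-month cap |
|---|---|---|---|
| 3 | 20.0% | 40.0% | 38.6% |
| 6 | 19.1% | 38.4% | 28.1% |
| 12 | 15.6% | 32.0% | 18.2% |

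Under the rule as written, the shortfall from 40% is 1.6 points for T = 6 (0.016 × 15 = 0.24 participants) and 8.0 points for T = 12 (0.080 × 15 = 1.2 participants). One participant of 15 is 6.7 points.

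**6. Whether waiting is feasible.** Closing every window needs T + 3.29 months from first dose: 9.3 months for T = 6, 15.3 for T = 12 and 27.3 for T = 24. This stays within 30 months for T up to about 26.7.

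**The case against.** The best defence is that the gap is narrow. Six months is a floor set by the last participant enrolled, so everyone before him contributes more. Short regimens may leave no window open. The Safety Assessment Committee reviews all safety data about every 3 months (SAP 4.3), and Protocol 4.5 counts receipt of safety follow-up data in defining the end of study. The study seeks preliminary estimates, and a shortfall of 1.6 points is small beside an interval of 16.3% to 67.7% for 6/15. Allowing an optional survival analysis does not forbid a safety update.

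Much of this stands and limits the size of the point. What remains is that committee review is monitoring and not a reported estimate, that permission by silence is not a specified analysis, and that sampling error is symmetric in intent whereas this error has a known direction.

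Three stronger readings are tempting, and the documents do not support them:

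- **That AE data are cut at 6 months.** SAP 3.4 sets a minimum, and SAP 5.5.2 has no upper time limit. Step 5 shows how far a hard-cap reading would overstate the loss.
- **That the Stage 2 expansion decision is biased.** SAP 3.4 and 5.7.1 base expansion on analyses before the primary one and on committee review, so the timing of the primary analysis cannot affect it.
- **That late immune-related events are the ones lost.** Neither document gives onset times. The supportable statement is only that the protocol itself chose a window of at least 100 days.

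**Conclusion.** The point holds in a limited form. Followed as written, SAP 3.4 can report the primary endpoint while some participants are still on treatment or within 100 days of last dose, and later AEs then have no planned table. Reported AE incidence is equal to or lower than the complete figure.

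The size cannot be fixed from these documents, because it depends on treatment duration and accrual. Under the assumed exponential durations (median 2–6 months, enrolment over 6–12 months), about 9–53% of a cohort has an open window at the trigger. A reader might take that range as the bias in AE incidence; it is not. Under fixed treatment of 6 or 12 months, 12-month accrual and a constant onset hazard, a true 40% risk shows as about 38% or 32%. With treatment of about 2.5 months or less there is no loss. The sample size, the Simon design and the Table 2 intervals are unaffected. The change is worth making because it is cheap and bears on the sole primary endpoint.

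**What to change.** In SAP 3.4:

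- State the data cut-off for the primary analysis of each cohort.
- Report at that analysis how many participants are still on treatment and how many are within 100 days of last dose.
- Specify a final run of the AE, SAE, treatment-related AE and discontinuation tables once the last participant's 100-day window has closed, and at the latest at cohort close. Report these as the final AE estimates for the cohort.

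The cost is one repeat of existing tables per cohort, and final AE rates that may be slightly higher than those first reported. No change to sample size, data collection or follow-up is needed.

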4 STUDY CONDUCT

4.1 Randomization Details

This is a non-randomized study. Assignment to one of the immunotherapy combinations will be made by the Investigator using his/her best clinical discretion based on the participant's medical history and disease status and knowledge of the available immunotherapy combination cohorts open for enrollment.

4.2 Blinding

This is an open-label study with no blinding.

4.3 Data Monitoring

To ensure careful review of the accumulating safety data for the PICI0033 platform study, a Safety Assessment Committee (SAC) will be established.

Ongoing safety data review will be conducted by the SAC for all cohorts. The PICI0033 SAC will have a core membership made up of genitourinary (GU) oncologists and immuno-oncologists and subject matter expert(s) as appropriate for a specific cohort (eg, vaccine expertise). Select Sponsor personnel, including the Medical Monitor and representatives from other functions including, but not limited to, Biostatistics, Clinical Science, and Pharmacovigilance, will be responsible for producing output for review and informing the SAC of any major safety signals in a timely manner.

To ensure participants' safety during the study, the SAC will meet approximately every 3 months to assess the totality of safety information in the clinical study across all cohorts. In addition, the SAC or the Sponsor may request ad hoc reviews at any time to address potential safety concerns.

Safety monitoring by the SAC will include unblinded evaluation of all AEs, SAEs, and laboratory data. If the SAC deems a benefit-risk assessment necessary, the SAC may also

review efficacy data. The SAC may recommend terminating a cohort or suspending enrollment for safety reasons. Roles and responsibilities of the SAC are detailed in a separate charter.

5 STATISTICAL ANALYSES

The data from each cohort will be analyzed independently of the other cohorts. Study conduct of one or more cohorts may be ongoing at the time of final analysis for a given cohort.

Summary statistics will be presented by cohort. Categorical variables will be summarized using frequencies and percentages. Continuous variables will be summarized using means, standard deviations, medians, interquartile ranges, minimums, and maximums.

5.1 Populations for Analysis

5.1.1 Evaluable Population

The evaluable population will serve as the primary population for the analysis of safety and efficacy data in this study. The evaluable population consists of all participants in a cohort who received at least 1 dose of any component of the combination study intervention. Participants will be grouped according to the cohort into which they were enrolled and dosed.

Efficacy analyses may be performed on a subset of the evaluable population, such as participants with measurable disease at baseline or participants with a baseline CTC value ≥ 5 cells/7.5 mL of blood. The specific analysis population used for each efficacy analysis is further detailed in Section 5.4.

5.2 Analysis of Study Conduct

The number of participants who were enrolled and treated, enrolled and not treated, and completed the treatment period will be presented in summary tables by cohort. The reason for treatment discontinuation and study discontinuation will be listed by participant and summarized in a table.

5.3 Analysis of Baseline Characteristics

Demographic and baseline characteristics of the study population will be summarized for each cohort. Variables to be summarized include, but are not limited to, age, sex, race, ethnicity, Eastern Cooperative Oncology Group (ECOG) performance status, cancer stage at initial diagnosis and enrollment, Gleason score, and PSA.

The baseline value of any variable will be defined as the last available value recorded prior to the first administration of study intervention.

5.4 Efficacy Analysis

The analyses for clinical activity will be performed on the evaluable population, consisting of all participants in a cohort who received at least 1 dose of any component of the combination study intervention. Some efficacy endpoints may be analyzed on a subset of the evaluable population, as summarized in Table 3.

This study is not intended or powered for hypothesis testing or comparison between cohorts. Due to the exploratory nature of this study, no control of type I error will be applied for any of the endpoints.

Table 3: Populations for Efficacy Analysis

Endpoint	Analysis Population
CRR	Evaluable population
CTC response (component of CRR)	Participants with a baseline CTC value ≥ 5 cells/7.5 mL of blood
PSA response (component of CRR)	Participants with a PSA value at baseline
ORR (component of CRR)	Participants with measurable disease at baseline per PCWG3-modified RECIST v1.1
DCR	Evaluable population
rPFS	Evaluable population
OS	Evaluable population
Change in CTC from baseline	Participants with a CTC value at baseline
CTC0	Participants with a baseline CTC value ≥ 1 cell/7.5 mL of blood
Percent change in PSA from baseline	Participants with a PSA value at baseline
Time to PSA progression	Participants with a PSA value at baseline
DOR	Participants with measurable disease at baseline per PCWG3-modified RECIST v1.1 and a best overall response of CR or PR

CR = complete response; CRR = composite response rate; CTC = circulating tumor cells; CTC0 = a measure of zero CTC; DCR = disease control rate; DOR = duration of response; ORR = objective response rate; OS = overall survival; PCWG3 = Prostate Cancer Clinical Trials Working Group 3; PR = partial response; PSA = prostate-specific antigen; RECIST = Response Evaluation Criteria in Solid Tumors; rPFS = radiographic progression-free survival

5.4.1 Primary Efficacy Endpoint

There are no primary efficacy objectives or endpoints for this study.

5.4.2 Secondary Efficacy Endpoints

Secondary efficacy endpoints include CRR, ORR, DCR, rPFS, and OS.

5.4.2.1 Composite Response Rate

CRR is a composite endpoint where response is defined as a participant meeting at least one of the following:

- CTC response: Change from unfavorable (≥ 5 cells/7.5 mL of blood) to favorable (≤ 4 cells/7.5 mL of blood). Participants with a missing baseline CTC value or baseline CTC value < 5 cells/7.5 mL of blood will not be evaluated for this criterion. The baseline CTC value is defined as the last available value recorded prior to the first administration of study intervention.
- PSA response: Confirmed PSA response is defined as $\geq 50\%$ reduction in PSA from baseline, with a repeat assessment confirming the result at least 3 weeks later. Participants without a PSA value at baseline will not be evaluable for this criterion. The baseline PSA value is defined as the last available value recorded prior to the first administration of study intervention.
- Objective radiographic response (ORR): Best overall response of CR or PR by objective radiographic disease assessment of soft-tissue, non-bone lesions, as determined by PCWG3-modified RECIST version 1.1. Per RECIST, to be assigned a best overall response of CR or PR, changes in tumor measurements must be confirmed by a repeat radiographic assessment performed no less than 4 weeks after the criteria for initial radiographic response were first met. In addition, responders must not have bone lesions that have progressed, as determined by PCWG3 criteria. Participants with measurable disease at baseline who received at least 1 dose of any component of the combination study intervention but do not have evaluable RECIST assessments for any reason will be counted as not responding. Participants without measurable, soft-tissue disease at baseline will not be evaluable for this criterion.

Response rates will be estimated within each cohort and 95% CIs will be estimated using the Clopper-Pearson method. Response rates and 95% CIs will also be presented for each individual criterion of CRR (CTC response, PSA response, and ORR).

